**Aim 2A: Examine whether an enhanced referral procedure results in higher rates of completed referrals to the CSC compared to standard referral procedures** by comparing rates of completed referrals in Phase I, standard care, versus Phase II, when an enhanced referral/linkage to care procedure is instituted in JJS. **2B: Identify implementation and service level factors that promote/hinder linkage to the CSC** by assessing feasibility, as determined by penetration (i.e. number of JJS personnel trained, and consistency in using the enhanced referral protocol) and acceptability (i.e., JJS staff perceived roles in screening and referral). Barriers and facilitators to linkage to CSC services will be examined as will equity of the linkage across gender, race, and ethnicity. Efficiency will be rated by the number of text message and phone contacts necessary to complete the referral to the CSC. These data will improve understanding of service level factors that influence implementation of these procedures, with implications for both a future trial and real world practice.

**Aim 3A: Investigate client level factors**, including attitudes about CSC referrals and the rates of treatment initiation/retention in CSC services. This data, collected at the 3 month follow-up, will also allow examination of the effects of the intervention on DUP as well as treatment barriers and motivation for treatment. **3B:**

**Investigate mental health indicators at follow-up** including psychotic symptoms and other outcomes (i.e., symptoms, social/role functioning), as well as juvenile justice contacts. **Aim 3C. Investigate the relationship between service mechanisms (treatment linkage/attendance) and psychotic symptoms/DUP.**

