#### **Phase II, months 20 – 31: Enhanced Referral/Linkage to Care condition.**

The Enhanced Referral/Linkage to Care condition follows the same steps as described in the Standard Care described above if there is imminent risk. If there is no imminent risk, the JJ intake worker contacts the CSC program directly for a "warm hand-off". The CSC intake worker will speak with the parent and arrange for an intake evaluation, either at the CSC clinic or at the family's home. For families that are already receiving mental health treatment, the JID intake worker will arrange the referral to the CSC for a consultation, at the CSC or family home. After the appointment is arranged, the JID intake worker reviews some psychoeducation material about the role of

mental health care in emotional/behavioral problems (see below).

In addition, the CSC clinician who takes the phone call will use a motivational interviewing style to encourage families to follow up with their scheduled appointment. This portion of the protocol is based on a module from PI [name]/Co-I [name]'s protocol that was recently tested in two randomized controlled trials (MH01783; AA020705) that are nearing completion (see below).

**Psychoeducation material.** The JID intake worker will review a handout on common symptoms of emotional distress and how youth and parents benefit from seeking mental health services. More specifically, the document outlines how to recognize warning signs of emotional distress, and the importance of finding support for difficulties that interfere with functioning and quality of life. We decided to use a generic description of emotional problems, including some psychosis-like experiences as well as other common concerns, rather than a description of specific psychosis-spectrum symptoms, because we believe it is more consistent with the level of training of JID workers and avoids the premature implication of a psychotic disorder diagnosis. In addition, to ensure these procedures can be easily disseminated in the future if they appear useful, we kept this aspect of the protocol very straightforward. The JID Intake worker will just be asked to read through the handout with the parent and not required to learn any interview material about mental health care or psychosis-spectrum symptoms. The review of the psychoeducation material will be presented with the goal of enhancing the chances that the family will follow through with the CSC appointment.

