**Motivational interviewing prompts.** Similar to the psychoeducation aspect of the protocol, the CSC clinician will not be required to learn any interview material but instead will have a sheet with the following prompts adapted from motivational interviewing protocols by Drs. [name] and [name]. The decision to keep this aspect of the protocol very structured was to ensure its eventual disseminability. Prompts include:

*Do you think it is necessary for your child to be seen at the clinic?*

*May I share a few concerns I have?*

*Some teens who have thoughts such as [specify] often get worse as they get older. For many teens, it's only temporary and they start to feel better after they start talking to someone.*

*And for some teens there are medicines that can help with these thoughts quite a bit.*

*Getting help for these thoughts early is important so we really encourage parents to get it checked out.*

*How are you feeling about going to the clinic appointment?*

*What might get in the way of you being able to do that (i.e., transportation, insurance, time of day)?*

*Is there anything we can do to help make it easier for you to get to the appointment?*

*We can call you the day before or the morning of the appointment to remind you -- would you like that?*

**Follow-up reminders to set up a CSC appointment.** Three and seven days after the referral to CSC, the JJ intake worker will text the teen's parent/caregiver to see if the family kept their appointment with the CSC. If not, the intake worker will text the parent the phone number for the CSC and will also ask permission to contact the CSC to further assist the family in setting up another appointment. JID workers can also choose to contact families by phone. A record of contacts will be recorded in order to examine feasibility, acceptability, and efficiency of these procedures.

[figure not shown]

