### **4. CMIR client (patient) level mechanisms**

**CSC services.** These data will be collected from the CSC with signed, written consent of the parent, and assent for those adolescents under age 18.

**Other non-CSC services.** *The Child and Adolescent Services Assessment* [CASA] is a parent-report instrument designed to assess at follow-up the use of mental health services for youth across 31 settings including inpatient, outpatient, and informal services. The measure has acceptable psychometric properties. Collateral information on treatment attendance (attendance at first treatment appointment and total number of treatment sessions attended) will also be collected by contacting each juveniles’ treatment provider at the 3-month follow-up. A release of information is requested at baseline, for both primary care physicians (PCP) and their mental health provider/agency, as part of the court intake process. The consent form will also contain language allowing the research team to collect this information from the youth’s treatment providers.

**Treatment motivation (self-report and parent/caregiver report).** The *Motivation for Youth’s Treatment Scale*, an 8-item measure, will be used to assess the youth’s motivation to engage in treatment at baseline and at follow-up. The total scale and two subscales (Problem Recognition and the Treatment Readiness) produce alpha coefficients of above .80.

**Barriers to treatment.** *The Barriers to Treatment Participation Scale*, a 44-item measure, will be completed at baseline and 3-month follow-up by caregivers to assess barriers that parents/caregivers experienced since intervention and the role those barriers may play in treatment engagement. Alpha coefficients range from 0.61 to 0.80.

**Treatment satisfaction** information will be gathered as part of the follow-up qualitative interview. Youth and caregivers will be interviewed about their satisfaction with the Enhanced Referral process as well as treatment at the 3-month follow-up.

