**Aim 2B: Identify implementation and service level factors that promote/hinder linkage to the CSC.** Feasibility and Penetration, the number and percentage of JID personnel trained and consistency (% of time) using the enhanced referral protocol will be calculated with descriptive statistics. A rate of 80% will be the benchmark. Efficiency will be rated by the number of text message and phone contacts necessary to complete the referral to the CSC. A benchmark of two contacts will be considered an indicator of efficiency. Equity of enhanced referral protocol fidelity and treatment linkage across gender, race, and ethnicity will be compared across Phase I (Standard Care) and Phase II (Enhanced Referral/Linkage to Care condition), as well as cross-sectionally in the Enhanced Referral/Linkage to Care condition only, using cross-tabulation approaches. Acceptability. JJS staff perceived roles in screening and referral will be reported in percentages based on qualitative interviews as well as by mean, median, and range of scores on the Attitudes toward Mental Health

Screening measure. A total of 80% of the JID personnel scoring within one standard deviation of the mean on this measure based on the literature will be the benchmark.

**Aim 3A: Investigate client level factors at follow-up.** Attitudes about CSC referrals. These analyses follow the qualitative interview procedure described above. Rates of treatment initiation/retention in CSC services or other mental health care. Percentages of CSC participation will be calculated with 80% set as the benchmark as will other types of mental health care as rated on the CASA. For those already in mental health care at the time of enrollment, percentages of consultation to the CSC will be calculated, as will the types of treatment received and frequency/intensity of the services. Treatment barriers and motivation. Scores on the *Motivation for Youth's Treatment Scale* and the *Barriers to Treatment Participation Scale* will be analyzed using a paired t-test to determine any changes in these measures from baseline to three month follow-up. Treatment Satisfaction. These analyses follow the qualitative interview procedure described above.

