The main outcomes are individual and total symptom scores (reflecting intensity, interference, and conviction) as well as diagnosis (i.e., low-risk, high-risk, or psychosis) and illness trajectory (i.e. progression, persistence, and partial or full remission) from the SIPS. We will also examine treatment attendance, motivation for treatment, and treatment barrier reduction. The analysis framework will be linear regression, with psychosis-spectrum symptoms as the outcome and Enhanced Referral/Linkage to Care condition as the main predictor. In a randomized design, we would be certain that randomization introduced control for measured and unmeasured factors. In the baseline control design, we cannot be sure that secular trends might not cause different kinds of adolescents to become referred to JJ and/or influence their responses to questions about psychotic-like symptoms. For this reason, we will control for a select set of *a priori* identified confounding variables (sex, gender, race, ethnicity, and age), past history of psychosis-spectrum symptoms, and ongoing mental health treatment at the time of enrollment. The sign and standard error of the enhanced referral/linkage to care condition describes the magnitude and significance of the treatment effect at the threshold level of the screen. For the purposes of this pilot, key outcome parameters are the standard deviation of the SIPS positive symptom scores, the pre-post correlation of the SIPS scores, and the overall  $R^2$  in follow-up SIPS scores given pre-specified covariates. These parameters would be necessary to estimate the sample size requirements for a definitive trial.

**Aim 3C. Relationship between service mechanisms (treatment linkage and attendance) and psychotic symptoms/DUP.** Correlation and regression techniques will be used to examine how use of services over the 3-month study period is related to change in psychosis-spectrum symptoms as assessed by the SIPS as well as general symptomatology, as assessed by the BPM.

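### The paired t-test named for the motivation and barriers scales has no phase term, so it cannot show whether the enhanced referral changed them, and Aims 3A and 3B need reconciling

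*Combined protocol and SAP*

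**What the plan says.** The Data Analysis Plan, Aim 3A, gives one test for the two scales: they "will be analyzed using a paired t-test to determine any changes in these measures from baseline to three month follow-up". It mentions neither phase nor condition and does not say whether the phases are pooled or tested separately.

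The Specific Aims describe the Aim 3A follow-up data as allowing "examination of the effects of the intervention on DUP as well as treatment barriers and motivation for treatment".

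The Measures section lists both scales under the heading "CMIR client (patient) level mechanisms". Motivation is reported by youth and caregivers, barriers by caregivers, each at baseline and 3 months. The section on baseline and follow-up assessment says that both phases complete the same assessments.

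The Phase II call is aimed at these two constructs. In the Enhanced Referral/Linkage to Care description, "the CSC clinician who takes the phone call will use a motivational interviewing style to encourage families to follow up with their scheduled appointment". The prompts include "What might get in the way of you being able to do that".

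Under Aim 3B the plan adds: "We will also examine treatment attendance, motivation for treatment, and treatment barrier reduction". The next sentence reads: "The analysis framework will be linear regression, with psychosis-spectrum symptoms as the outcome and Enhanced Referral/Linkage to Care condition as the main predictor".

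**The concern.** A paired test asks whether scores moved between the first visit and 3 months. The planning question is whether they moved differently under the enhanced referral than under standard care. Court monitoring, the CSC referral given in both phases, regression to the mean and the passage of time could all shift motivation or perceived barriers without any contribution from the call or the handout.

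Elsewhere the plan names its contrast when it wants one: linkage under Aim 2A is compared across phases by logistic regression. For these scales the only named test has no comparison, and the Aim 3B regression is not clearly extended to them. At stake is whether the team designing the larger trial learns if the motivational component acts on the mechanisms it was built to change.

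**Working it through.** **Inputs from the plan.** 70 enrolled per phase and 80% follow-up (Estimated sample size and retention rates). 0.80 × 70 = 56 per phase and 0.80 × 140 = 112 in total, against the plan's approximately 55 and 110; these agree to rounding. The plan gives no SD, correlation, effect size or significance level for these scales.

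**Assumptions.** Unit SD at each visit, bivariate normal scores, pre-post correlation r = 0.3, 0.5 or 0.7, two-sided 5%, 55 per phase.

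**Step 1: change over time, no referral effect.** The SD of change is √(2(1 − r)) = 1.183, 1.000, 0.775. For a common change d, the paired t statistic is noncentral with parameter d√n / √(2(1 − r)). With d = 0.3 and n = 110 this is 2.66, 3.15, 4.06; with n = 55 it is 1.88, 2.22, 2.87.

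| Probability of a significant result | r = 0.3 | r = 0.5 | r = 0.7 |
|---|---|---|---|
| Pooled paired test, d = 0.3 | 0.750 | 0.877 | 0.981 |
| Paired test in one phase, d = 0.3 | 0.455 | 0.589 | 0.805 |
| Pooled paired test, d = 0.2 | 0.420 | 0.547 | 0.766 |
| Paired test in one phase, d = 0.2 | 0.234 | 0.308 | 0.468 |

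In the same settings a contrast between phases is significant about 5% of the time by simulation, with or without first-visit adjustment.

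**Step 2: running the test per phase.** If p is the single-phase probability, Phase II is significant and Phase I is not with probability p(1 − p). At d = 0.3 this is 0.248, 0.242, 0.157, although the phases do not differ.

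**Step 3: the converse.** With changes of −0.25 and +0.25 in the two phases (SD of change 1, a true phase difference of 0.5), the pooled paired test is significant in 4% of simulated trials and the between-phase test in 74%.

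**Step 4: precision of a phase contrast.** For unadjusted 3-month scores the 95% half-width is 1.982 × √(2/55) = 0.378 SD. Adjusting for the first-visit score multiplies this by about √(1 − r²), giving 0.361, 0.327, 0.270 SD.

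**Step 5: adjust for the first visit or not.** Simulated with 20,000 trials per cell for the adjusted contrast; closed form for the unadjusted one. Carry-over is the share of the 0.5 SD effect already present at the Phase II first visit.

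| Setting | Unadjusted | Adjusted (r = 0.3 / 0.5 / 0.7) |
|---|---|---|
| 0.5 SD effect, no carry-over | 0.738 | 0.777 / 0.853 / 0.954 |
| 0.5 SD effect, one quarter carried over | 0.738 | 0.708 / 0.740 / 0.850 |
| 0.5 SD effect, half carried over | 0.738 | 0.625 / 0.601 / 0.651 |
| 0.5 SD effect, all carried over | 0.738 | 0.452 / 0.304 / 0.184 |
| No effect, stable cohort difference 0.2 SD | 0.180 | 0.121 / 0.090 / 0.073 |
| No effect, stable cohort difference 0.3 SD | 0.345 | 0.198 / 0.142 / 0.102 |

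Neither choice is better in every row.

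**The case against.** **The contrast may already be intended.** Aim 3B mentions motivation and barrier reduction immediately before a framework with condition as main predictor, and the Approach says that the two conditions will be compared. One can read the plan as describing the scales within person under Aim 3A and comparing them by condition under Aim 3B. This stands in part. A reader might infer that no phase comparison of these scales was ever planned, and the documents do not support going that far. But the framework sentence names only psychosis-spectrum symptoms as its outcome, so the intention is not written down.

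**The purpose is open to two readings.** The Specific Aims sentence could mean effects on DUP, with barriers and motivation merely described. That is possible, though less natural given how the scales are classed and what the Phase II call targets. A paired t-test is a valid answer to the descriptive question.

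**The percentages are power, not error.** This is right. A reader might take 75–98% as the false-positive rate of the planned test. It is the chance of detecting a real 0.3 SD change. It misleads only if the result is presented as a referral effect, and Aim 3A does not say that it will be. Likewise, the 16–25% for significance in Phase II alone needs an inference rule that the plan does not state.

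**Adjustment is a matter of judgement.** Cohort difference is the threat that the plan itself names: "we cannot be sure that secular trends might not cause different kinds of adolescents to become referred to JJ". Early effect at the Phase II first visit is only an inference. The fidelity section places the baseline assessment typically within a week of the intake appointment and has caregivers report then what the CSC worker told them, so that visit may follow the hand-off. How much scores would have moved by then is unknown. The documents therefore do not support insisting on the unadjusted contrast as the main one.

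**Conclusion.** The concern holds in a limited form. The one test named for the motivation and barriers scales describes change and cannot attribute it to the enhanced referral, whether pooled or run by phase. Aims 3A and 3B give different accounts of how these scales will be analysed and must be reconciled.

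The finding about wording and estimand rests on the text alone. The percentages rest on the assumed SD, correlations, change sizes and significance level, and serve only as illustration.

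The consequence is minor. This is a planning study, no benchmark or decision is attached to these scales, and the key parameters listed under Aim 3B concern SIPS scores. The disclaimer about estimating effect size is written for Aim 3B, yet that aim still specifies a regression on condition, so the disclaimer is no reason to leave the contrast out here. The change is still worth making: both phases already supply both time points, and a small edit lets the plan address its own question.

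**What to change.** In Aim 3A, regress the 3-month motivation scores (youth and caregiver report) and the 3-month barriers score on phase, with the covariates already listed under Aim 3B: sex, gender, race, ethnicity, age, past history of psychosis-spectrum symptoms, and ongoing mental health treatment at enrollment. Report each estimate with its 95% confidence interval. Keep the paired change within each phase as description only. In Aim 3B, state that the regression on condition covers these two scales.

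Report the contrast with and without adjustment for the first-visit score, and have the sponsor's statistician name the main one in advance. Adjustment gains precision and reduces bias from cohort differences, but it may remove part of the effect if the Phase II first visit follows the hand-off.

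The cost is wording; no new data are needed. The contrast rests on a non-randomised, earlier-phase control exposed to secular drift, as the plan already accepts for Aims 2A and 3B. It is also imprecise, at about ±0.38 SD unadjusted, and should be reported as such.

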**Aim 3B: Investigate mental health indicators at follow-up.** Psychosis-spectrum symptoms will be assessed on the SIPS (which will also allow examination of the effects of the intervention on DUP, DUI, and functioning) and other clinical outcomes on the subscales of the BPM. The goal of this aim is to obtain a reasonably precise estimate of the standard deviation for the outcome variables, and pre-post correlations of outcome variables, which are essential statistics for powering a definitive trial. Following Leon and colleagues (2011) and Kraemer and colleagues (2006), our goal is not to obtain a preliminary estimate of the treatment effect size, but as per Teare and colleagues (2014), the size of the pilot we propose is sufficient to obtain sufficiently precise estimates of key variance and covariance parameters necessary to design a definitive trial. Our approach will be to conduct an analysis consistent with the testing of the hypothesis that JJS youth enrolled in the Enhanced Referral/Linkage to Care condition will have fewer psychosis-spectrum symptoms and other clinical outcomes at 3 month follow-up relative to youth in the baseline control.

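### The Aim 3B phase comparison of 3-month symptom scores does not name the baseline score as a covariate, although it is collected in both non-randomised phases, and 'past history' is left undefined

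*Combined protocol and SAP*

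**What the plan says.** In the Data Analysis Plan, Aim 3B, the hypothesis is that Phase II youth have fewer symptoms at 3 months than Phase I youth. This compares follow-up levels, not change. The model is stated as: "The analysis framework will be linear regression, with psychosis-spectrum symptoms as the outcome and Enhanced Referral/Linkage to Care condition as the main predictor".

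The plan explains why it adjusts. Without randomisation, "we cannot be sure that secular trends might not cause different kinds of adolescents to become referred to JJ", and such trends may also "influence their responses to questions about psychotic-like symptoms". The controls are sex, gender, race, ethnicity and age, plus "past history of psychosis-spectrum symptoms, and ongoing mental health treatment at the time of enrollment". No baseline score appears in the list, and no section says how the history variable is coded.

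The section on baseline and follow-up assessment says that both phases complete the same battery at both visits, covering psychosis-spectrum symptoms, general psychiatric symptoms and functioning. The SIPS description separates the current rating at each interview from a retrospective timeline of onset.

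Aim 3B says of its purpose that "our goal is not to obtain a preliminary estimate of the treatment effect size". The key pilot parameters are the SD of the SIPS positive symptom scores, "the pre-post correlation of the SIPS scores, and the overall" R-squared given the pre-specified covariates. Even so, the sign and standard error of the condition term are said to be what "describes the magnitude and significance of the treatment effect at the threshold level of the screen".

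**The concern.** The phases differ in calendar time, and the plan itself expects that case mix may drift. The baseline value of the outcome is the most direct available measure of whether one phase enrolled more severely affected youth, and it is usually the strongest predictor of the follow-up value. Leaving it out has three possible consequences:

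- the phase coefficient absorbs baseline severity differences that were measured and could have been removed;
- its standard error is larger than it need be;
- the R-squared passed on to the definitive trial may omit a likely strong predictor.

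The undefined history covariate decides how much of this applies to the SIPS models. If it is the baseline SIPS score, they are already adjusted. If it is a lifetime yes/no item or an onset date, they are adjusted only weakly. In neither case does it give like-for-like control for the BPM or functioning scales, which Aim 3B also covers.

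The point does not extend to outcomes that already refer to baseline, such as "illness trajectory (i.e. progression, persistence, and partial or full remission) from the SIPS" or reduction in treatment barriers.

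**Working it through.** **The plan's own figure.** The Power paragraph gives 140 at baseline and 110 at 3 months, and the sample-size section gives about 55 completers per phase at 80% follow-up. 140 × 0.80 = 112 and 70 × 0.80 = 56, so the figures reproduce to within two participants. No alpha, power or effect size is given for Aim 3B.

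**Assumed inputs.** The documents do not give the pre-post correlation r, the baseline difference between phases, or the correlation h between the history covariate and the baseline score. I use r = 0.3 to 0.8 and outcomes in SD units.

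**Precision.** With no overlap from the history covariate, the SE with baseline divided by the SE without it is √(1 − p²), where p is the partial correlation of baseline with outcome. If history correlates h with baseline and acts on the outcome only through it, the ratio is √[(1 − r²)/(1 − h²r²)]. Percentage cuts in SE:

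| r (or p) | no overlap | h = 0.7 | h = 0.9 | h = 1 |
|---|---|---|---|---|
| 0.3 | 4.6 | 2.4 | 0.9 | 0 |
| 0.5 | 13.4 | 7.5 | 3.0 | 0 |
| 0.7 | 28.6 | 18.1 | 8.0 | 0 |
| 0.8 | 40.0 | 27.6 | 13.5 | 0 |

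The lost degree of freedom hardly matters: at n = 110, with an assumed 10 versus 11 parameters, the first column becomes 4.1, 13.0, 28.2 and 39.7.

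In absolute terms, with 55 per phase and no other covariates, the SE without baseline is √(2/55) = 0.191 SD. With baseline it is 0.165 at r = 0.5 and 0.136 at r = 0.7. At an assumed two-sided 5% level and 80% power, the detectable difference is (1.96 + 0.84) × SE. That is 0.53 SD without baseline, and 0.46 or 0.38 SD with it.

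**R-squared.** Counting only history and baseline, R-squared is (hr)² without baseline and r² with it. At h = 0.7 this is 0.12 versus 0.25 (r = 0.5) or 0.24 versus 0.49 (r = 0.7). A trial sized on the lower value alone would be larger by (1 − h²r²)/(1 − r²) = 0.8775/0.75 = 1.17, or 0.7599/0.51 = 1.49.

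**Bias.** Take an observed baseline difference d = 0.2 SD that the listed covariates do not capture, and no true phase effect.

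| Source of the difference | without baseline | with baseline |
|---|---|---|
| (a) severity, baseline without error | dr = 0.06 to 0.16 | 0 |
| (b) severity, baseline reliability L = 0.8 | dr/L = 0.075 to 0.20 | dr(1/L − 1) = 0.015 to 0.04 |
| (c) pure shift in reporting at both visits | d = 0.20 | d(1 − r) = 0.14 to 0.04 |

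In (b), 20% of the bias remains after adjustment. In (c), adjustment helps little when r is low. The reliability of 0.8 is an assumption: the nearest figure in the protocol is a training ICC above .8 for the SIPS rater in a previous team, which is not the reliability of the scores in this study.

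Simulation of (a) with 55 per phase (4,000 runs per setting) gave bias of 0.100 at r = 0.5 and 0.145 at r = 0.7 without baseline, and 0.000 and 0.002 with it. Adding a yes/no history proxy, with an assumed latent correlation of 0.5 with baseline, lowered the first two only to 0.083 and 0.117. Formulas (b) and (c) agreed with a simulation of 400,000 participants to within 0.01.

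**The case against.** The strongest reply is that this is mainly an undefined covariate rather than a shown omission. The Specific Aims say that the research assessment, with the SIPS and other measures, is meant to capture the history of psychotic symptoms, so a SIPS-derived history covariate is a natural reading. If it is the baseline score, the SIPS models gain nothing from the change. That stands for SIPS, and it is why the gain is shown as running down to zero. It does not supply a baseline covariate for BPM or functioning.

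Second, no pilot decision rests on this coefficient. The aim disclaims an effect size, and the SD and pre-post correlation do not depend on the covariate list. That also stands and limits the impact. But the plan still reads magnitude and significance from the phase term, and the exploratory moderator analyses repeat the main models and base inference on effect sizes for interactions.

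Third, the 17% or 49% sample-size penalty arises only if planners ignore the pre-post correlation reported beside R-squared. That is largely correct, and the penalty should not be counted as a likely cost.

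Fourth, baseline is not cleanly before exposure in Phase II. The hand-off happens at intake, and the baseline assessment typically falls within a week of it. This is a real but modest reservation, and a sensitivity model without baseline helps to check it.

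**Conclusion.** The concern holds for the continuous follow-up scores: SIPS symptom scores, BPM subscales and the two functioning scales. The baseline score is not named, it is available in both phases, and the history covariate is undefined.

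All sizes are conditional on assumed inputs. The SE reduction ranges from nothing (history is the baseline SIPS score) to about 40% (partial correlation 0.8). For a 0.2 SD severity difference that the listed covariates miss, adjustment removes a bias of 0.06 to 0.16 SD if baseline is measured without error, and about 80% of the bias at reliability 0.8. It removes only part of a shift in how youth answer symptom questions, which is the second of the plan's two stated worries, and nothing of unmeasured secular confounding.

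The practical impact is limited by the pilot's purpose, but the change should be made because it costs almost nothing and follows from the plan's own reason for adjusting. Confidence is medium, mainly because the intended meaning of the history covariate cannot be settled from the documents.

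**What to change.** In the Data Analysis Plan, Aim 3B:

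1. Add the baseline value of the same measure to each continuous model: the same SIPS score, the same BPM subscale or the same functioning scale.
2. Define the history covariate by source, time window and coding, so that it does not duplicate the baseline score.
3. Report R-squared with and without baseline, and keep the model without baseline as a sensitivity analysis.
4. State that baseline adjustment only partly removes a secular shift in reporting or a difference measured with error, and does not remove unmeasured secular confounding.
5. As a separate, minor wording correction, replace the sentence on the sign and standard error. Condition is set by calendar phase, so the coefficient is not an effect at a screening threshold, and a sign with a standard error gives no magnitude. Suggested text: the phase coefficient and its 95% CI estimate the adjusted mean difference between phases among enrolled screen-positive youth.

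The cost is a change of wording and one degree of freedom per model. No new data are needed. The one drawback is that Phase II baseline reporting could be slightly affected by the hand-off, which the sensitivity model in item 3 helps to check.
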